7.0 Safety Reporting

Trial protocol deviations which have been recorded for each centre, with reasons and participant trial status outcomes, will be tabulated: see Table 16. Then the number, impact of protocol deviation and proportion of participants experiencing a protocol deviation will be summarised for the trial as a whole and per treatment group: see Table 17.

Table 16: Protocol Deviation.

Number	Nature of	Site	Trial Arm	Deviation	Trial Status
	Deviation			Impact	
1					
2					
Total					

Trial Arm: Intervention or Control, Deviation Impact: 1=Completeness of trial data, 2= Reliability of trial data, 3=Primary outcome, 4= Accuracy of trial data, 5= participant rights, safety, 6=no impact

Table 17: Summary Table of Protocol Deviations

Total	Intervention	Control
n	n (%)	n (%)

Number of Protocol		
Deviations		
Number of participants		
with a protocol		
Deviation		
Deviation of Impact		
1.Completeness		
2.Reliability		
3.Primary outcome		
4.Accuracy		
5.Participant		
6.No impact		
Total		
	NA	

All AEs and SAEs will be described, including their nature, severity, relatedness to the intervention and outcome on participant trial status; See Table 18 and 19. This includes details such as any unplanned hospital admission connected to adverse events. The number and proportion of participants experiencing an AE or SAE during the trial will be summarised by treatment group. Depending on the amount of data, a logistic regression model adjusted for recruiting centre will be used to compare the rates in the two groups. Deaths are not anticipated in this study, but details of any that do occur will be reported.

Table 18: Adverse Events.

Number	Nature of Event	Severity	Status of Event	Causality (Related or Unrelated)	Trial Status
1					

2			
Total			

Severity 1=mild, 2=moderate, 3=severe, 4= not known. Status: 1=resolved, 2=recovered with sequalae, 3=ongoing, 4=not known. Causality: Related=1, unrelated=0.

Table 19: Serious Adverse events.

Number	Nature of Event	Status Of Event	Causality (Related or Unrelated)	Hospital stay * (days)	Trial Status
1					
2					
Total					

Status: 1= resolved, 2=recovered with sequalae, 3=ongoing, 4= fatal, 5= Not known. Causality:

related=1, unrelated=0. *Hospital admission if applicable/ data available.

Table 20: Comparison of adverse events between groups.

	Total n	Intervention n (%)	Control n (%)	OR (95% CI)*	p-value
Number of SAEs					
Number of participants with serious adverse events					
Number of AEs					

Appendix A.

MCID sub-study statistical analysis plan

The aim of this sub-study is to estimate the MCID of the TUG test and the QUALEFFO-41 questionnaire. In addition to the key outcome measures (TUG and QUALEFFO-41), the following variables will be used as anchors:

TUG test anchors:

- 1. Global rating change (GRC) scale of walking and balance self-reported rating at 4 months
- 2. Timed Loaded Standing (TLS) test change between scores at 4 months and baseline
- 3. Physical Function (PF) domain of QUALEFFO-41 change between scores at 4 months and baseline.

QUALEFFO-41 anchors:

- 1. GRC scale of quality of life self-reported rating at 4 months
- 2. TLS test change between scores at 4 months and baseline
- 3. EQ-5D-5L change between overall health scale at 4 months and baseline

Participants will be included in the analysis if they have complete baseline and 4-month data for target outcomes and their respective anchors variables. For this sub-group we will perform descriptive statistics (mean and standard deviation (SD), median and interquartile range (IQR), or percentage, where appropriate) for sex, age, height, weight, BMI, comorbidities score, BMD, and T-score lumbar spine.

We will then perform multiple Pearson's correlation analyses for the key outcome measures and each of their corresponding anchors. Anchors that do not show at least a moderate correlative relationship (r>0.4) with their key outcome measure will not be included in further MCID analyses.

We will calculate the change between 4-month scores and baseline for both key outcome measures and eligible anchor variables, excluding GRC scales as they are self-reported only at 4 months.

From the 4-month GRC scores and the change scores calculated from the other anchor variables, we will dichotomise data into 'responder' or 'non-responder' based on the following:

- a) GRC is a 7-point scale: -3 (much worse), -2 (moderately worse), -1 (a little worse), 0 (no change), 1 (a little better), 2 (moderately better), 3 (much better); scores >0 will be labelled as a 'responder' and scores ≤0 labelled as a 'non-responder'.
- b) TLS is a strength test where longer duration indicates stronger musculature; calculated change scores >0 seconds will be labelled as a 'responder' and ≤0 seconds labelled as a 'nonresponder'.
- c) PF domain of the QUALEFFO-41 is a questionnaire where a *lower* score indicates better physical aspects of quality of life; calculated change scores <0 will be labelled as a 'responder' and scores ≥0 labelled as a 'non-responder'.

d) ED5Q overall health scale is reported on a visual analogue scale from 0-100, where 100 indicates best health; calculated change scores >0 will be labelled as a 'responder' and scores ≤0 will be labelled as a 'non-responder'.

Based on these dichotomised data, we will perform anchor-based analyses for the TUG and QUALEFFO-41 using each eligible corresponding anchor variable. Methods of anchor-based analysis will include:

- a) Average Change (AC) the average score change of the responders, according to the anchor.
- b) Change Difference (CD) the average score of change of responders (according to the anchor) minus the average score of change of non-responders.
- c) Receiver-operating characteristic (ROC) analysis a plot of sensitivity against specificity using dichotomised data from each anchor. We will use Youden's J statistic and Euclidean distance to determine the optimal cut-off values, and also calculate the area under the curve (AUC).

In addition to the anchor-based methods, we will estimate the MCID with distribution-based analysis by calculating 0.5SD of the TUG and QUALEFFO-41 change scores (between baseline and 4 months).

Key outcome	Corresponding	Method of analysis				
measure	anchor	AC (s)	CD (s)	ROC (s)	0.5 SD (s)	
	GRC					
TUG	PF					
	TLS					
	GRC					
QUALEFFO-41	EQ-5D					
	TLS					

Example Table A: MCID values for key outcome measures

Example Table C: ROC analyses

Key outcome measure	Corresponding anchor	Youden's J statistic	Euclidean distance	AUC
TUG	GRC			
	PF			
	TLS			
QUALEFFO-41	GRC			
	EQ-5D			
	TLS

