Conservative treatment for osteoporosis includes bone protective medications and lifestyle adaptations.[3] Guidelines recommend people with osteoporosis keep active and exercise to slow the rate of bone loss, to maintain muscle strength and physical function and to prevent falls and further fractures.[2-5] Multiple randomized controlled trials (RCTs) have investigated the efficacy of exercise for people with VFFs and reported short-term, post-treatment benefits to pain, strength, spinal posture, balance, fear-of-falling, mobility and QoL. [4-6] A Cochrane systematic review in 2019 concluded there is moderate-quality evidence that exercise improves physical function.[4] However, treatment effects are often small and difficult to sustain. [4, 6] Adherence, or the extent to which patients engage in treatment, has been identified as an important issue by many studies, with adherence to clinic-based exercise protocols often around 50% and lower for unsupervised home exercise. [4-7] Partial or non-adherence is associated with worse outcomes and conversely higher adherence with better outcomes. [4, 6, 7] Adherence is a critical consideration because it affects exercise dose. For example, in the PROVE trial benefits associated with exercise at 4 months were not sustained at 12 months, whilst those who attended more sessions experienced better outcomes.[6] Higher adherence has been associated with greater treatment effects but studies monitoring adherence show exercise compliance declines after supervised interventions cease. [7, 8] When assessing intervention efficacy, it is also important to know the minimal clinically important difference (MCID) of any outcome measure in the population concerned, which is defined as the smallest difference in score which a patient perceives as beneficial.[9] A recent Cochrane review identified the Quality-of-Life Questionnaire (QUALEFFO-41) and the Timed Up and Go (TUG) test as important outcome measures targeted by exercise interventions in people with VFFs and also recognised that their MCIDs were unknown.[4]

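### The exploratory MCID analysis requires complete data on all anchors of an outcome before anchors are screened, so a GRC-anchored estimate loses participants over variables it does not use

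*SAP*

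**What the plan says.** Appendix A names three anchors for each target outcome. For TUG they are the GRC for walking and balance, the TLS change and the QUALEFFO-41 physical function change. For QUALEFFO-41 they are the GRC for quality of life, the TLS change and the EQ-5D-5L health scale change. TLS is thus an anchor for both outcomes.

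The steps then run in this order:

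1. Inclusion: "Participants will be included in the analysis if they have complete baseline and 4-month data for target outcomes and their respective anchors variables".
2. Description of that set: "For this sub-group we will perform descriptive statistics".
3. Screening: "We will then perform multiple Pearson's correlation analyses for the key outcome measures and each of their corresponding anchors". The discard rule follows: "Anchors that do not show at least a moderate correlative relationship (r>0.4) with their key outcome measure will not be included in further MCID analyses".
4. Estimation: average change, change difference and ROC cut-offs, computed separately for each anchor that passes, plus 0.5 SD of the outcome change score.

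No step redefines the set after screening or says that completeness is judged pair by pair. Example Table A has no column for n. Elsewhere, SAP section 4.3 puts the trial's main analyses on an available-case basis. SAP section 2.2 lists the MCID objective as exploratory.

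**The concern.** The inclusion rule asks for more data than any single estimate needs. The GRC-anchored QUALEFFO-41 estimate shows this most clearly: both of its variables are self-reported, yet a participant enters only with a back-endurance test at two visits and an EQ-5D-5L health score at two visits. If TLS then fails the correlation screen, it plays no part in any estimate but has already removed people from all of them.

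The certain cost, if any anchor data are missing, is precision. The GRC estimate is a bad place to lose it, because SAP section 2.1 describes the MCID as a score difference, "which is defined as the smallest difference in score which a patient perceives as beneficial", and of the listed anchors only the GRC asks patients directly about change they perceive.

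**Working it through.** **Data required and data used.**

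| GRC-anchored estimate | Needed for the estimate | Also demanded by the inclusion rule |
|---|---|---|
| TUG | TUG at 0 and 4 months; GRC at 4 months | TLS at 0 and 4 months; physical function at 0 and 4 months |
| QUALEFFO-41 | QUALEFFO-41 at 0 and 4 months; GRC at 4 months | TLS at 0 and 4 months; EQ-5D-5L health scale at 0 and 4 months |

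The 0.5 SD estimate needs no anchor. It appears to be restricted in the same way, since no other set is defined.

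**Does the wording allow another reading?** The word *respective* could mean all anchors of both outcomes, or only the three anchors of the outcome concerned. TLS is on both lists, so under either reading a participant without it leaves both GRC estimates. Only a pair-by-pair reading would avoid this. The SAP does not state one, and the single sub-group described before screening points away from it.

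**Number of participants available.** The SAP gives no sample size for the MCID sub-study, so the trial figures in section 3.3 serve as bounds. They reproduce. With a difference of 1.4 s, SD 2.5 s, two-sided 5% and 80% power, the t-based solution is 51.03 per arm, rounded up to 52; 52 per arm gives 80.7% power. Then 104 / 0.90 = 115.6, rounded up to 116. The number evaluable at 4 months is taken to lie between 104 and 116.

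**Cost to a GRC estimate.** Let t be the share of otherwise evaluable participants without a TLS change score, and p the share without the third anchor's change score. Both are assumptions. Taking the two as independent:

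- share kept = (1 − t)(1 − p)
- SE ratio = 1 / √(share kept), treating the SE as proportional to 1/√n

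| Assumed missing | Share kept | Lost of 104 | Lost of 116 | SE ratio |
|---|---|---|---|---|
| none | 1 | 0 | 0 | 1.00 |
| TLS 5% only | 0.95 | 5.2 | 5.8 | 1.026 |
| TLS 10% only | 0.90 | 10.4 | 11.6 | 1.054 |
| TLS 5%, third anchor 5% | 0.95² = 0.9025 | 10.1 | 11.3 | 1.05 |
| TLS 10%, third anchor 10% | 0.90² = 0.81 | 19.8 | 22.0 | 1.11 |

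**Could the estimate also shift?** An illustrative simulation assumed 15% missing TLS, a TUG change SD of 1.5 s and a latent correlation of 0.5 between TUG change and perceived change. When missingness was unrelated to TUG change, neither average change nor change difference moved. When it was concentrated in those who improved least, average change went from −1.10 s to between −1.17 and −1.22 s, and change difference from −1.19 s to between −1.16 and −1.10 s.

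**The case against.** A common complete-case set is a legitimate design. Example Table A puts anchors and methods side by side. With one sample, differences between rows reflect the anchor and not who happened to be measured, and one descriptive table covers everyone analysed. This stands, and is a reason to keep that set as a sensitivity analysis. It does not justify making it the only set, particularly when it is conditioned on anchors that may be discarded.

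The loss may also be small. SAP section 3.6 has one outcome package completed at each visit, so missingness may fall largely by whole visit; someone with TUG and GRC at 4 months may well have the rest. Section 4.3 applies validated item-level methods to QUALEFFO-41, which limits loss of the physical function score. Both points stand. They make the independence assumption doubtful and the two-anchor figures closer to an upper illustration.

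A reader might infer that the rule tilts the GRC estimate towards fitter people, since TLS is a loaded physical test. The SAP does not support stating this as a fact. It gives no TLS missingness and does not say whether someone unable to do the test is missing or scored at or near zero seconds. In the simulation the shifts were modest, moved the two methods in opposite directions, and arose only under assumed selective missingness.

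**Conclusion.** The point holds as a correctable weakness in an exploratory analysis. The order of steps and the absence of re-admission are explicit, and the list-wise reading is the natural one. For TLS alone at an assumed 5-10% missing, the SE of the GRC estimate rises by about 3-5%. The 5-11% range requires a second anchor to be missing at the same rate, independently, and should not be attributed to TLS. With complete anchor data the cost is nil. Bias towards fitter participants remains conjecture.

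A reader might also conclude that the plan is wrong to set several anchors and methods beside each other without naming a lead estimate. That is a separate and more debatable matter: reporting several is a recognised approach, and the GRC itself could fail the r>0.4 screen. The trial's primary and secondary treatment comparisons are untouched.

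**What to change.** Replace the inclusion sentence in Appendix A with: *For each outcome-anchor pair, all participants with baseline and 4-month data for that outcome and that anchor (4-month only for GRC) will be included; the 0.5 SD estimate will use all participants with baseline and 4-month data for the outcome.* Add n to each row of Example Table A. Keep the all-anchor complete set as a sensitivity analysis, so that anchors can still be compared on a common sample.

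The cost is a reworded inclusion rule, a column and a repeat run on data already being collected. The downside is that n differs between rows of the main table, and the descriptive table must say which set it describes.

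Optional: given the definition in section 2.1, name the GRC-anchored estimate as the lead one for each outcome if GRC passes the r>0.4 screen, and state in advance what will be reported if it does not.

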3.3 Sample size

The primary outcome is the TUG test, a test of balance, lower limb strength and walking ability with established reliability and validity. It records the time in seconds (s) a person takes to stand up from a chair, walk 3 metres at a self-selected speed, turn and walk back and sit down, faster performance indicates better function. [10, 15] The MCID for the TUG has not been established in people with VFFs, but a MCID of 1.4 s is reported for similar older populations with chronic musculoskeletal disorders.[22] The study requires 104 participants (52 per arm) to be 80% powered to detect a 1.4s difference in TUG score between groups at a 5% significance level (two sided) assuming that the SD is 2.5s. Similar trials have had loss to follow-up rates of 10% at 12 months. To account for this the sample size is 116 participants (58 per arm).

Sample size calculations were performed in Stata v15 (StataCorp. 2017. *Stata Statistical Software: Release 15*. College Station, TX: StataCorp LLC).

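### The MCID anchor screen is printed as r>0.4 without an absolute value and placed before the change scores, so applied as written it drops oppositely scored anchors and screens on outcome level

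*SAP*

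**What the plan says.** Appendix A names three anchors for each key outcome. For TUG they are the GRC of walking and balance, change in TLS, and change in the QUALEFFO-41 Physical Function (PF) domain. For QUALEFFO-41 they are the GRC of quality of life, change in TLS, and change in the EQ-5D-5L overall health scale.

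The steps then run in this order:

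1. Correlate: "We will then perform multiple Pearson's correlation analyses for the key outcome measures and each of their corresponding anchors".
2. Screen: anchors that "do not show at least a moderate correlative relationship (r>0.4) with their key outcome measure will not be included in further MCID analyses".
3. Compute change: "We will calculate the change between 4-month scores and baseline for both key outcome measures and eligible anchor variables", leaving out the GRC scales.
4. Dichotomise each anchor into responders and non-responders, then apply average change, change difference and ROC analysis. A 0.5 SD distribution-based estimate is added.

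The stated scale directions are:

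- **TUG** (section 3.3): "faster performance indicates better function", so fewer seconds is better.
- **GRC** (Appendix A): "scores >0 will be labelled as a 'responder' and scores ≤0 labelled as a 'non-responder", so higher is better.
- **TLS** (Appendix A): "TLS is a strength test where longer duration indicates stronger musculature", so higher is better.
- **EQ-5D-5L overall health** (Appendix A): 100 is best, so higher is better.
- **QUALEFFO-41 PF** (Appendix A): "calculated change scores <0 will be labelled as a 'responder' and scores ≥0 labelled as a 'non-responder", so lower is better.
- **QUALEFFO-41 total and sub-scales** (section 2.2): higher is better, which conflicts with the PF entry in Appendix A.

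**The concern.** There are two separate difficulties.

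**Sign.** Pearson's r carries a sign. The cut-off has no absolute value, no expected direction is given, and the scales are not aligned before correlating. Where improvement lowers the outcome and raises the anchor, a good anchor gives a negative r and cannot exceed 0.4.

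**Level or change.** When the screen runs, the plan has not yet calculated change in TUG or QUALEFFO-41, and it calculates anchor change only for anchors already judged eligible. Yet TLS, PF and EQ-5D are listed as changes, and GRC is itself a rating of change. The text does not say whether the outcome enters as baseline value, 4-month value or change. The order of steps points to level, while the MCID methods that follow all work on change.

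The screen decides which anchors feed every anchor-based MCID. If the sign reading, the level-or-change question and the scoring direction are settled only with data in hand, each choice can alter which anchors survive.

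**Working it through.** The 0.4 cut-off is a chosen threshold, so there is no figure of the plan's to reproduce. The check uses the stated directions and two short calculations.

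**1. Expected sign of each pair, outcome and anchor both taken as change (GRC as rated).** The conflict over QUALEFFO-41 gives three possible scorings:

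| Pair | (a) lower better throughout | (b) higher better throughout (section 2.2) | (c) total higher better, PF lower better |
|---|---|---|---|
| TUG–GRC | − | − | − |
| TUG–TLS | − | − | − |
| TUG–PF | + | − | + |
| QUALEFFO–GRC | − | + | + |
| QUALEFFO–TLS | − | + | + |
| QUALEFFO–EQ-5D | − | + | + |
| TUG anchors able to pass r>0.4 | 1 of 3 | 0 of 3 | 1 of 3 |
| QUALEFFO anchors able to pass r>0.4 | 0 of 3 | 3 of 3 | 3 of 3 |

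TUG loses GRC and TLS in every column. The rest depends on the scoring.

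**2. What the absolute value changes.** By Fisher's z, SE = 1/√(N−3). Take N = 104 (the section 3.3 requirement; the number available at 4 months is not given), so SE = 1/√101 = 0.0995. Assume a true r of −0.5; the SAP gives no correlations.

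- atanh(0.4) = 0.4236 and atanh(0.5) = 0.5493.
- Under |r|>0.4: (0.4236 − 0.5493)/0.0995 = −1.26, so the chance of passing is 0.897.
- Under signed r>0.4: (0.4236 + 0.5493)/0.0995 = 9.78, so the chance is about 7 × 10⁻²³.

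For an assumed true r of −0.6 the chances are 0.997 and about 2 × 10⁻²⁹. For −0.3, the chance under |r|>0.4 is 0.126, so the absolute value still screens out weak anchors.

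**3. What the level-or-change question changes.** Let B and F be baseline and 4-month TUG with equal SD s and correlation ρ, and D = F − B. Suppose GRC relates to TUG only through change: GRC = aD + e, with e independent of B and F.

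- Var(D) = 2s²(1−ρ) and Cov(D, F) = s²(1−ρ).
- Hence corr(GRC, F) = corr(GRC, D) × √((1−ρ)/2).

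With corr(GRC, D) = −0.5:

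- ρ = 0.5: √0.25 = 0.5, giving −0.25.
- ρ = 0.8: √0.10 = 0.316, giving −0.16.

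Both fail even |r|>0.4. If GRC tracked change perfectly, passing would need √((1−ρ)/2) > 0.4, so (1−ρ)/2 > 0.16 and ρ < 0.68. Using baseline TUG instead gives the same size with the opposite sign, since Cov(D, B) = −s²(1−ρ). The SAP gives no ρ, so these values are illustrations. They show that adding an absolute value does not by itself repair the rule.

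**The case against.** The plan nowhere says that the sign of r is to count. Requiring at least a moderate relationship is a statement about strength, and a strongly negative r meets it. The responder rules follow each anchor's own direction, so the authors knew that the scales run in opposite directions, and the example tables keep rows for all six pairs. An analyst who found r = −0.6 between TUG and GRC would be unlikely to discard GRC. This stands: |r|>0.4 is the probable intent, and the sign problem is one of wording applied literally.

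A reader might go further and infer that one key outcome must end with no anchor. The documents do not support that. It follows under scoring (a) or (b), but Appendix A gives lower-is-better only for PF, and the only direction stated for the total is the one in section 2.2. Under that mix, scoring (c), both outcomes keep at least one anchor.

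A reader might also infer that the MCID objective cannot be met. That is too strong as well, because the 0.5 SD estimates for both outcomes do not pass through the screen.

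On level versus change, it is fair that the anchors are already defined as changes and that the plan never expressly says outcome levels are correlated. What remains is the outcome side: it is called only a measure, and its change is calculated after the screen. That does not depend on how the sign is read.

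**Conclusion.** The point holds as a defect in how the screening rule is written. Followed literally, it excludes at least GRC and TLS for TUG because of their direction, and it screens change-type anchors against outcome level. The other four pairs depend on the unresolved QUALEFFO-41 direction.

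The sign result rests only on the scale directions the SAP states. The size of the level effect rests on assumptions: equal SDs, GRC related to TUG only through change, and illustrative values of ρ and of the GRC–change correlation.

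The reach is limited to the anchor-based estimates of an exploratory sub-study. The 0.5 SD estimates and the treatment comparisons in section 6 are untouched. It should be fixed, because the rule gates every anchor-based MCID and is cheap to correct, but it does not threaten the main trial.

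**What to change.** In Appendix A:

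- Move the calculation of baseline-to-4-month change ahead of the screen, for both key outcomes and for TLS, PF and EQ-5D overall health.
- Restate the screen: keep an anchor if |r|>0.4, in the expected direction, between the change in TUG or QUALEFFO-41 and the anchor (the 4-month GRC rating, or the change in TLS, PF or EQ-5D overall health).
- Reconcile the QUALEFFO-41 scoring direction between section 2.2 and Appendix A, so that the expected directions can be fixed in advance.

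A rank correlation (Spearman) for the 7-point GRC is an optional refinement. The cost is a few sentences, with no new data.

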3.1 Study Design

OPTIN is a two-arm, parallel group, superiority randomised controlled trial (RCT) with blinded assessments. It includes a nested evaluation of the MCID of key outcome measures. All patients receive treatment, either a standardised package of physiotherapy exercise rehabilitation or the same exercise rehabilitation integrated with an exercise behaviour change intervention (OPTIN intervention). The primary outcome is the TUG measured at 12 months post-randomisation. All clinical outcomes are collected at baseline (0) and 4-, 8- and 12-months following randomisation.

The trial will take place in at least 6 NHS hospitals across the UK and their related physiotherapy services and via video-call in participant homes. Each site will recruit participants, undertake measures and provide the intervention and comparator. A trial research clinician (TRC) will collect

data at research assessments, following a standardised format and using outcome measures that are valid and reliable with this patient population. Measures are a mix of self-report questionnaires and measures of physical function, including monitoring adverse events and intervention adherence.

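### MCID sub-study: the Youden and Euclidean ROC cut-offs depend on the share of responders, so they estimate the perceived-benefit threshold only when that share is near 50%

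*SAP*

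**What the plan says.** Section 2.1 of the SAP sets the target. The MCID is the quantity "which is defined as the smallest difference in score which a patient perceives as beneficial".

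Appendix A dichotomises each anchor at zero. For the GRC, any rating above no change makes a responder. For TLS, the physical function domain of the QUALEFFO-41 and the EQ-5D health scale, any change in the favourable direction does. The ROC step then uses Youden's "J statistic and Euclidean distance to determine the optimal cut-off values". Example Table A shows the ROC value as an MCID estimate beside the average change in responders (AC), the difference in change between responders and non-responders (CD), and half an SD.

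Section 3.1 describes the sample: "All patients receive treatment, either a standardised package of physiotherapy exercise rehabilitation", or the same rehabilitation with the behaviour-change component. There is no untreated group.

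The SAP gives no expected responder share for any anchor, does not plan to report it, does not adjust the ROC cut-off for it, and does not say how the several estimates will be combined.

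**The concern.** The ROC cut-off is the only planned method that looks for a threshold on the change scale, so readers are likely to take it as the MCID. It answers a different question, however: at what change does a patient's chance of feeling better equal the response rate in this sample? If the response rate is far from 50%, the answer moves away from the typical threshold, and it would differ in another trial with another response rate, even if patients judged benefit in exactly the same way.

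At stake is whether the TUG and QUALEFFO-41 values from this sub-study can be carried over to other studies. Different responder shares across anchors could also create differences between the rows of Example Table A that have nothing to do with the anchors' meaning.

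**Working it through.** **The plan's own figure.** The SAP gives none for the ROC cut-off. Its sample size (section 3.3) supplies n and a yardstick. It is "80% powered to detect a 1.4s difference in TUG score between groups", "assuming that the SD is 2.5s". The normal formula gives 2 × (1.960 + 0.842)² × 2.5² / 1.4² = 50.1, so 51 per arm. With the t distribution, power is 79.97% at 51 and 80.7% at 52, which reproduces 104; 104/0.9 = 115.6 gives 116.

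**Identity.** Youden's J is maximal where the change-score densities of responders and non-responders are equal, f₁(c) = f₀(c). By Bayes' rule P(R|c)/p = (1 − P(R|c))/(1 − p), hence P(R|c) = p.

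**Model.** All of the following are assumptions, not SAP figures. Change is expressed as seconds faster. Observed change has mean μ and SD σ = 1.5 s. Individual thresholds are normal with mean M = 1.0 s. ρ_T is the correlation of true change with the latent rating (0.70 or 0.55), R is the reliability of the change score, and ρ = ρ_T√R. Then:

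- mean change μ = M + z_p σ√R/ρ_T
- Youden cut-off c = μ − z_p σ(1 − √(1 − ρ²))/ρ
- change at responder probability 0.5: h = μ − z_p σ/ρ

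**Effect of p, error-free scores (R = 1).** Here c = M + z_p s, with s = σ√(1 − ρ²)/ρ. This gives s = 1.5 × 0.714/0.70 = 1.53 s and 1.5 × 0.835/0.55 = 2.28 s.

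| p | z_p | c, ρ_T 0.70 | c, ρ_T 0.55 |
|---|---|---|---|
| 50% | 0 | 1.00 s | 1.00 s |
| 60% | 0.253 | 1.39 s | 1.58 s |
| 70% | 0.524 | 1.80 s | 2.19 s |
| 80% | 0.842 | 2.29 s | 2.92 s |

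Simulated medians at n = 104 agree: about 1.0 s at 50%, 1.8 to 2.2 s at 70% and 2.2 to 2.8 s at 80%, with Euclidean values nearly the same.

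**Effect of unreliable change scores, p = 70%** (ρ_T 0.70 / 0.55).

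| R | mean change | Youden c | 0.5 point h |
|---|---|---|---|
| 1.0 | 2.12 / 2.43 s | 1.80 / 2.19 s | 1.00 / 1.00 s |
| 0.8 | 2.01 / 2.28 s | 1.73 / 2.07 s | 0.75 / 0.68 s |
| 0.7 | 1.94 / 2.20 s | 1.69 / 2.00 s | 0.60 / 0.49 s |
| 0.5 | 1.79 / 2.01 s | 1.59 / 1.85 s | 0.21 / −0.01 s |

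For R of 0.5 to 0.8 the Youden value is thus about 1.5 to 2.0 s to within 0.1 s. If 0.55 to 0.70 is instead read as the correlation with observed change, it is lower: simulated medians of 1.44 to 1.71 s at R = 0.7.

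**A second parameter set.** With true threshold 1.4 s, true-change SD 1.7 s, error SD 0.9 s and ρ = 0.66, only p varies:

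| p | mean change | Youden | Euclidean |
|---|---|---|---|
| 30% | 0.21 s | 0.59 s | 0.65 s |
| 50% | 1.40 s | 1.40 s | 1.40 s |
| 70% | 2.59 s | 2.21 s | 2.17 s |
| 80% | 3.31 s | 2.69 s | 2.62 s |

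The bias runs in both directions and vanishes at 50%. At p = 80% the Youden value lies (2.69 − 1.4)/(3.31 − 1.4) = 67% of the way from the threshold to the mean change. With other settings of this model this is 87% at ρ = 0.44 and 40% at ρ = 0.85.

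**The case against.** *Sensitivity and specificity do not depend on prevalence.* That does not help here. Responder status is itself a cut on a continuum of improvement, so the change distributions of both groups move when mean change moves.

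*The direction and size are assumed.* This stands. The SAP gives no p and no reliability for TUG change. The argument for p above 50% concerns the GRC; nothing comparable can be said for TLS, physical function or EQ-5D change. The scenarios also imply large mean improvements (2.1 to 2.4 s at p = 70%, error-free), while section 2.1 says that exercise effects are often small.

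*The benchmark is a 50% point, which the SAP's definition does not name.* True, but the ROC rule corresponds to no fixed percentile either; its percentile is whatever p happens to be.

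*The obvious replacement has its own faults.* This also stands. A reader might infer that the change at fitted logistic probability 0.5 should replace the ROC value. It is biased low with unreliable scores (last column of the reliability table). At p = 70%, its root mean square error is about level with Youden's at reliability 0.7 and correlation 0.55 (1.09 against 1.13 s) and worse at reliability 0.5 (1.06 to 2.13 against 0.74 to 1.01 s). It can also be negative. With mean change 1.0 s, p = 70% and observed correlation 0.70 or 0.55, it is 1.0 − 0.524 × 1.5/0.70 = −0.12 s or 1.0 − 0.524 × 1.5/0.55 = −0.43 s, against 0.68 to 0.76 s for Youden.

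*ROC is one of several exploratory estimates.* Correct, and this limits the consequences. The other columns do not repair it: AC averages all improvers and also rises with p, and neither CD nor half an SD aims at a threshold.

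**Conclusion.** The point holds as a conditional limitation of one method in an exploratory sub-study. The dependence on p follows from the definition of Youden's rule and needs no assumption about the trial; the Euclidean rule shows it numerically, so using both gives no independent check. The sizes are illustrative: for a true threshold of 1.0 s at p = 70%, about 1.8 to 2.2 s without measurement error and about 1.5 to 2.0 s at reliability 0.5 to 0.8.

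Two stronger readings are not supported. A reader might infer that the ROC value must be too high because all participants are treated. The documents make p above 50% plausible for the GRC but do not establish it; at 50% there is no bias, and below 50% the bias reverses. A reader might also infer that the cut-off simply estimates the mean improvement. That is close for the moderate anchors that the r > 0.4 screen admits; with strong anchors the cut-off lies around midway between threshold and mean change or nearer the threshold.

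The trial's primary analysis and sample size are untouched. The change is worth making because it affects what the sub-study can claim.

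**What to change.** In Appendix A:

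1. Report the responder number and share p for each anchor, in Example Tables A and C.
2. Beside the ROC cut-offs, add an estimate from the same dichotomised data that accounts for p: the change at fitted logistic probability 0.5, a predictive-modelling estimate adjusted for the proportion improved, or both, with bootstrap 95% confidence intervals.
3. Label the Youden and Euclidean cut-offs as dependent on p, and state that they will not be interpreted as the MCID on their own when p is far from 50%.
4. Do not make the logistic 0.5 point the sole threshold. State that it is biased low when change scores are unreliable and can be negative when mean change is small and p is high.

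The cost is a few lines of code and extra table columns. No new data are needed.
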